4.1.15. Handling of Incomplete or Missing Dates Associated with an Event

An incomplete date occurs when the exact date an event (e.g. an adverse event) occurred or ended cannot be obtained from a subject. The database contains data fields for month, day, and year. A date is incomplete if at least one of these three fields is not known.

For many of the planned analyses, a complete date is necessary to determine if the event should be included in the analysis (e.g. if the event is treatment-emergent) or to establish the duration of an event. In such cases, incomplete dates will be imputed as described below.

For the purposes of handling partially reported start and stop dates for an event the following algorithm will be applied:

- Missing start day, but month and year present:
 If the event occurs same month and year as the occurrence of IMP, then the start day of the event will be assigned to the day of first dose of IMP (i.e., Day 1).
 Otherwise the start day will be set to the first day of the month.
- Missing start day and month, but year present:
 If event occurs in the same year as IMP, then the start date of the event will be assigned to Day 1.
 Otherwise the start day and month will be set to 01 January.
- In the unlikely event of a completely missing start date (year not present), the start date will be imputed as Day 1.
- Missing end day, but month and year present:
 The day will be set to the last day of the month.
- Missing end day and month, but year present:
 The end day and month will be set to the date of study completion. However, if study completion year is greater than the year of the event, then the day and month will be set to 31 December.
- Missing all components of an end date and the event is not marked as ongoing:
 The event will be considered as ‘ongoing’ and will be considered treatment-emergent if the start date is on or after Day 1.

If any imputed start date causes the start date to occur after the end date, the end date will be used for the imputation of the start date. If any imputed end date causes the end date to occur prior to the start date of the event, the start date of the event will be used for the imputation of the end date. If the imputed date is later than the date of study withdrawal, then the date of study withdrawal will be used to impute the date in question. In subject data listings, start and stop date of events will be displayed as reported on the eCRF without imputed dates.

For the purposes of handling partially reported diagnosis date of Parkinson's disease, the following algorithm will be applied to randomized subjects:

- Missing day, but month and year present:

If the diagnosis date occurs same month and year as the occurrence of the subject's screening date, then the day of the diagnosis date will be assigned to the day of the subject's screening date.

Otherwise the diagnosis day will be set to the first day of the month.

- Missing day and month, but year present:

If the diagnosis date occurs in the same year as the occurrence of the subject's screening date, then the diagnosis date will be assigned to the subject's screening date.

Otherwise the diagnosis day and month will be set to 01 January.

- In the event of missing year or a completely missing diagnosis date, the diagnosis date will be assigned to the subject's screening date.

In subject data listings, diagnosis dates will be displayed as reported on the eCRF without imputed dates. For screen failures, no imputation will be made to the date of diagnosis of Parkinson's disease.

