5.1 Inclusion Criteria

Subjects are eligible to be included in the trial only if all of the following criteria apply:

General and Administrative	
1.	Male and female subjects aged 40 to 80 years, inclusive, at the time of signing the ICF.
2.	Sexually active men or women of childbearing potential must agree to use acceptable (at minimum) or highly effective birth control, as defined in Section 10.4 (Appendix 4), or remain abstinent during the trial and for 4 weeks after the last dose of trial treatment.
3.	Subjects who are capable of giving signed informed consent as described in Section 10.1.3 (Appendix 1), which includes compliance with the requirements and restrictions listed in the ICF and in this protocol.
4.	Subjects who are able, in the opinion of the investigator, to understand the nature of the trial and comply with protocol requirements, including the prescribed dosage regimens, scheduled visits, laboratory tests, and other trial procedures.
Parkinson's Disease Diagnosis	
5.	
Subjects with a diagnosis of PD that is consistent with the UK Parkinson's Disease Society Brain Bank diagnostic criteria.
 
Note: Subjects having more than one affected relative (Step 2 UK Parkinson's Disease Society Brain Bank exclusion criterion) but meeting all other criteria consistent with the UK criteria will be considered to have met eligibility criteria for a diagnosis of PD (Litvan et al, 2003; Massano and Bhatia, 2012).
 
Note: Motor asymmetry may or may not be present at the time of Screening, and is not an explicit requirement for inclusion, as long as the subject meets the UK Parkinson's Disease Society Brain Bank diagnostic criteria based on medical history or physical examination.

6.	Subjects with modified Hoehn and Yahr stage 1, 1.5, or 2.

7.	Subjects with disease duration (from time of diagnosis) of <3 years and disease progression in the 3 years before signing the ICF.
8.	Subjects with an MDS-UPDRS Part II score ≥ 2 and Part III score ≥ 10 at the Screening Visit and at the Baseline Visit.
9.	Subjects with early PD who, in the opinion of the investigator, require pharmacologic intervention for disease management.

Concomitant Parkinson's Disease Medications

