5.9.4. Subgroup Analyses

Subgroup analyses of the primary endpoint will be made based on the mITT set to assess consistency of the intervention effect across the following subgroups:

- Age group: < 65 vs \geq 65 years
- Sex: female vs male
- Hoehn and Yahr Status at screening: 1 vs 1.5 vs 2
- Baseline MDS-UPDRS Part II score: \leq baseline median vs $>$ baseline median (median of the mITT set regardless of treatment group)
- Baseline MDS-UPDRS Part III score: \leq baseline median vs $>$ baseline median (median of the mITT set regardless of treatment group)
- Use of concomitant MAO-B inhibitor: yes vs no
- Years since initial diagnosis: (<1 year vs 1 to < 2 years vs 2 to < 3 years)
- Race: white vs other
- Region: United States vs Non-US

If the number of subjects within a subgroup is too small (less than 10% of the mITT set), the subgroup categories may be redefined prior to unblinding the study or the specific subgroup analysis may not be performed. Provided that the sample sizes in the subgroups allow, the MMRM analysis method described in [Section 5.9.2](#) will be applied to the subgroup analysis (excluding the covariate of MAO-B inhibitor use in the MAO-B subgroup models). The treatment effect across subgroups will be summarized by forest plots.

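### A year-only diagnosis date from the third calendar year before screening is imputed to 3 years or more, and the years-since-diagnosis subgroup has no category for it

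*SAP*

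**What the plan says.** SAP 4.1.15 has a separate rule for partial diagnosis dates, and "the following algorithm will be applied to randomized subjects". Its branches are:

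- **Year only, earlier than the screening year:** "Otherwise the diagnosis day and month will be set to 01 January".
- **Year only, same year as screening** (the branch that begins "If the diagnosis date occurs in the same year as the occurrence of"): the screening date is used.
- **Month and year, day missing:** the first of the month, or the screening day if the month and year are those of screening.
- **No year** ("In the event of missing year or a completely missing diagnosis date"): the screening date is used.

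Protocol 5.1, criterion 7, admits "Subjects with disease duration (from time of diagnosis) of <3 years and disease progression in the 3 years before signing the ICF".

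SAP 5.9.4 defines the subgroup as "Years since initial diagnosis: (<1 year vs 1 to < 2 years vs 2 to < 3 years", with no category for 3 years or more and none for unknown. Its only flexibility is that "the subgroup categories may be redefined prior to unblinding the study" when a subgroup holds less than 10% of the mITT set. SAP 5.10 to 5.12 apply the same factor to the key secondary and other secondary endpoints, and SAP 5.6 summarises years from diagnosis at baseline. Neither document states the reference date for years since diagnosis.

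**The concern.** The imputation rule, the entry criterion and the subgroup cut-offs do not fit together. In the quoted branch, 1 January is never later than the true date, so duration can only be lengthened, and nothing limits it to the range that the entry criterion allows. A subject known to be under 3 years can therefore receive an analysis value that no subgroup category accepts. In the other direction, a subject whose diagnosis year is unknown is given zero duration and counted as under 1 year.

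At stake are the classification and completeness of one subgroup factor across several endpoints, and the baseline description of disease duration. If the gap is found only when the analysis is run, the programmer must decide without a rule where these subjects go.

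**Working it through.** The plan gives no figure on this point, so there is nothing to reproduce. The check is date arithmetic on the rules above.

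**Boundary check, reference date = screening.** Let Y be the screening year.

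| Diagnosis year (year only) | Imputed date | Imputed duration over all screening days | Result |
|---|---|---|---|
| Y | screening date | 0 | shortened; stays under 1 year |
| Y-1 | 1 Jan Y-1 | 1.00 to 1.996 years | always 1 to <2 |
| Y-2 | 1 Jan Y-2 | 2.00 to 2.998 years | always 2 to <3 |
| Y-3 | 1 Jan Y-3 | 3.00 to 3.997 years | never in a category |

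Example for Y-3: diagnosed 1 October 2019, screened 15 June 2022. True duration is 2.70 years; imputed duration is 3.45 years.

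Example for a missing day: diagnosed 20 June 2019, screened 15 June 2022. The true duration is 5 days short of 3 years. The imputed date of 1 June 2019 gives 3 years and 14 days.

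**Expected shares.** Assumptions, not in the documents: screening falls at a fraction s of the year, uniform on 0 to 1; true duration D is uniform on 0 to 3 years; whether a date is partial does not depend on D.

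- Shares by diagnosis year: Y is s/3, averaging 1/6; Y-1 is 1/3; Y-2 is 1/3; Y-3 is (1-s)/3, averaging 1/6.
- No category: all of Y-3 = 1/6 = 16.7%. This is half of those truly at 2 to <3 years (1/6 out of 1/3).
- Moved up one category: Y-1 with D<1 and Y-2 with D<2, each (1-s)/3, averaging 1/6; together 33.3%.
- Wrong category in total: 1/6 + 1/6 + 1/6 = 50%.
- Mean error in duration: -1/18 (Y) + 1/6 (Y-1) + 1/6 (Y-2) + 1/9 (Y-3) = 7/18 = 0.39 years too long.

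Enumerating calendar dates for screening in 2020 to 2023 gives 16.5% and 49.8%, in agreement.

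**Month-and-year dates.** The same argument over 36 months gives 1/72 = 1.4% with no category and 3/72 = 4.2% in the wrong one.

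**Reference date.** If duration is counted to a baseline visit 28 days after screening, 19.0% of year-only dates lose their category. However, 2.5% would do so even with complete dates.

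**Number of subjects.** The count of partial dates is unknown. For illustration, out of the 522 planned:

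| Assumed year-only share | Year-only dates | No category (1/6) | Wrong category in total (1/2) |
|---|---|---|---|
| 0% | 0 | 0 | 0 |
| 1% | 5.2 | 0.9 | 2.6 |
| 2% | 10.4 | 1.7 | 5.2 |
| 5% | 26.1 | 4.4 | 13.1 |

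**The case against.** The strongest objection is that Y-3 is the one year for which the year alone cannot show that criterion 7 is met. The protocol forbids waivers (Section 5) and requires screening evaluations to be reviewed to confirm eligibility (Section 8.1). A site enrolling such a subject should have known at least the month, so year-only Y-3 records may be the rarest kind and 17% may be too high. This is inference, but reasonable. It does not remove the misclassification: with no Y-3 records at all, the wrong-category share is (1/6 + 1/6) / (1/6 + 1/3 + 1/3) = 40% of the year-only dates that remain.

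It can also be said that the rule is prespecified, identical across arms and close to the SAP's convention for event start dates. That is true, and it keeps the consequences small. But an event start date has no matching upper limit on duration; here the entry criterion supplies one and the rule ignores it.

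A reader might infer that affected subjects become ineligible or count as protocol deviations. The documents do not support this. Eligibility is settled at screening, listings show the reported date without imputation, and neither the analysis populations (SAP 5.2) nor the deviation review (SAP 5.16) refers to the imputed date. A reader might also infer that every year-only date is lengthened, or pushed past 3 years. Same-year dates are shortened, and at screening only Y-3 crosses the limit.

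**Conclusion.** The point holds, and it is minor. For a year-only date from the third calendar year before screening, the loss of a category is certain, and the 10% redefinition clause does not cover it. A month-and-year date can do the same at the boundary. Dates from the two preceding years can only move up one category; dates in the screening year, or with no year, receive zero duration.

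The shares of about 17% without a category and 50% in the wrong one rest on the uniform assumptions and apply to year-only dates alone. The number of subjects cannot be found from the documents and may be small or zero. It would be wrong to read this as a threat to the main results: time since diagnosis is not in the primary or key secondary models (SAP 5.9.2, 5.10.1.1, 5.10.2.1), so those tests do not change.

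**What to change.** Replace the diagnosis-date paragraph of SAP 4.1.15, before unblinding, with a rule on these lines:

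- State the reference date for years since diagnosis. It should be the date at which criterion 7 is judged; otherwise even complete dates can pass 3 years.
- For a partial date, take the reported year or month, restrict it to dates strictly less than 3 years before the reference date and no later than screening, and impute the midpoint of what remains.
- For a date with no year, do not assign zero duration. Report it as unknown in the baseline summary and leave it out of this subgroup.

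Under the same assumptions, no year-only date is left without a category. The wrong-category share falls to 1/12 (Y-1) + 1/12 (Y-2) = 1/6, about 17%, and the mean error is near zero. The bound must be strict, because a date exactly 3 years back still fails a limit of less than 3 years. An unbounded 1 July would leave about 4% without a category. Keeping 1 January with a strict floor would leave none without a category but about 33% in the wrong one.

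The cost is one SAP paragraph, and any subject with no diagnosis year drops out of this one subgroup analysis.

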4.1.16. Handling of Alphanumeric Data

Should there be instances where a clinical laboratory parameter is reported with imbedded non-numeric characters, as for example, “<0.1” or “>10”, the data will be imputed as described below for quantitative summaries. The actual alphanumeric values as reported in the database will be presented in data listings.

- The values < LLN will be replaced with $\frac{1}{2}$ the value of the lower limit. For example, “< 0.1” will be replaced with 0.05 if the LLN is 0.1.
- The values > ULN will be replaced by values of increased precision by one level. For example, “>0.1” will be imputed to “0.11” if the ULN is 0.1, and “>10” will be imputed to “10.1” if the ULN is 10.

Additionally, in the event of the upper limit of normal (ULN)/lower limit of normal (LLN) reported as alphanumeric (e.g., ‘<5’, ‘≤5’, ‘>5’, ‘≥5’), the determination of the laboratory abnormality severity grade will be based on the convention on the ULN and LLN below:

- If the ULN is in the form of ≤ 5 , only the numeric part will be used for determining the abnormality severity grade of the test results (i.e., the ULN is set to 5). If the ULN is in the form of <5, the numeric value of the ULN will be decreased by two levels of precision in the direction of the symbol (i.e., the ULN is set to 4.99).

- If the LLN is in the form of ≥ 5 , only the numeric part will be used for determining the abnormality severity grade of the test results (i.e., the LLN is set to 5). If the LLN is in the form of >5 , the numeric value of LLN will be increased by two levels of precision in the direction of the symbol (i.e., the LLN is set to 5.01).

4.2. Visit Windows

Data collected longitudinally across visits will be summarized and analyzed by visit.

Laboratory data will be presented according to the nominal visit as collected from the eCRF or laboratory data unless the visit is an early termination or unscheduled visit. Early termination and unscheduled visits will be assigned visit windows based on the study day completed according to **Table 3**. Baseline will be determined per the baseline definition in [Section 4.1.7](#). Other assessment data, including efficacy assessments data, will be mapped to the appropriate time point based on the window as defined in **Table 3** from Baseline to Week 22 to appropriately captured time of assessment in cases of visit schedule variations. Due to the short interval between Visit 10 (Week 26) and Visit 11 (Week 27), data obtained at the nominal visit at this two time points will be used with the exception of early termination/unscheduled visits.

Table 3: Visit Windows

Analysis Visit	Analysis Visit Target Day	Analysis Visit Window
Baseline	1	≤ 1
Day 1*	1	1
Week 2	14	2 - 24
Week 5	35	25 - 45
Week 8	56	46 - 66
Week 11	77	67 - 86
Week 14	98	87 - 111
Week 18	126	112 - 140
Week 22	154	141 - 168
Week 26	182	169 - 185
Week 27	189	186 and higher

* Day 1 assessments are pre-IMP except ECG with a 60 minute post-dose assessment

If assessments are collected multiple times within a given visit window the result closest to the analysis visit target day will be used for summary presentations. If two measurements have the same distance to the target day, the later value will be used. If a subject has multiple non-missing values on the same date, the average record will be used (if applicable). If there are multiple average records on the same date, the average based on the scheduled measurements will be used. If no averages exist, the last record as determined by the time collected will be used.

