The ECG results will be evaluated at the investigational site to determine the subject's eligibility and to monitor safety during the trial. The principal investigator (or qualified designee) will review, sign, and date each ECG reading, noting whether or not any abnormal results are of clinical significance. The ECG will be repeated if any results are considered to be clinically significant. A central ECG service will be used for reading all ECGs to standardize interpretations for the safety analysis.

If, during screening, any abnormal ECG finding is deemed medically significant (impacting the safety of the subject or the interpretation of the trial results) or meets an exclusion criterion (see [Section 5.2](#)), the subject should be excluded from the trial. Medically significant or exclusory abnormal results on an ECG at screening should be

repeated with 2 additional ECG recordings to ensure reproducibility of the abnormality, and the 3 ECG recordings read by the central service to confirm the abnormality before excluding a subject. For subjects with a QTcF >450 msec at screening, a subject will be excluded if the QTcF intervals reported by the central service are >450 msec for 2 or more of the 3 ECG recordings, unless due to ventricular pacing. If, at the Baseline Visit, the QTcF interval is >450 msec on the machine readings, consult the medical monitor to determine whether the subject remains eligible to be randomized while awaiting the readings from the central service.

Exclusion criteria for screening do not apply as mandatory discontinuation criteria for subjects who are already randomized. A repeat ECG should be performed to confirm any clinically significant abnormality that is identified in a randomized subject during the treatment period (which will be confirmed by central service read) and, in these cases, the medical monitor should be consulted on the appropriateness of the subject continuing in the trial.

[figure not shown]

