8.3.7 Clinical Safety Laboratory Assessments

[figure not shown]
The list of clinical laboratory tests that are to be performed is provided in [Section 10.2](#) (Appendix 2). All protocol-required laboratory assessments must be conducted in accordance with the laboratory manual and the Schedule of Assessments ([Table 2](#)).

The investigator must review the laboratory report, document this review, and record any clinically relevant changes occurring during the trial in the AE section of the eCRF. The laboratory reports must be filed with the source documents. Clinically significant abnormal laboratory findings are those that are not associated with the underlying disease, unless judged by the investigator to be more severe than expected for the subject's condition.

All laboratory tests with values that are considered clinically significantly abnormal during participation in the trial should be repeated until the values return to normal, to baseline, or are no longer considered clinically significant by the investigator or medical monitor. If such values do not return to normal/baseline within a period of time judged reasonable by the investigator, the etiology should be identified and the sponsor notified.

All protocol-required laboratory assessments, as defined in [Section 10.2](#) (Appendix 2), must be conducted in accordance with the laboratory manual and the Schedule of Assessments ([Table 2](#)).

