4.1.7. Baseline Value

For purposes of analysis, the baseline value of a given assessment is defined as the last value obtained prior to initiation of IMP. Should the Day 1 visit value be obtained after the first dose of IMP or if this value is not available at Day 1, the most recent value obtained prior to the first dose of IMP will be used for the baseline value.

For US subjects with triplicate ECGs taken at 3 pre-dose timepoints, the baseline value will be defined as the average of the available pre-dose ECG values (i.e. triplicate ECGs at -45 minutes pre-dose, -30 minutes pre-dose, and -15 minutes pre-dose). For non-US subjects, the baseline value will be defined as the average of the available pre-dose ECG values. Scheduled records will be selected over unscheduled records if a tie breaker is needed.

For blood pressure and heart rate measurements, baseline is defined as the average of the duplicates at the last visit prior to the IMP administration. If no duplicate is available, the last non-missing value prior to the initiation of IMP will be used.

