5.14.7. Electrocardiograms (ECGs)

Single or triplicate 12 lead ECGs will be obtained during the trial. All ECG recordings will be obtained after the subject has been supine and at rest for at least 5 minutes. A triplicate set of ECGs is 3 consecutive ECGs collected 1 to 2 minutes apart over a 5 minute period. Any values taken in triplicate will be averaged for analysis. ECGs and corresponding changes from baseline will be summarized by treatment group and visit using descriptive statistics. Average records will be used for the analysis where available.

The number and percentage of subjects who experience any post-baseline occurrence of potentially clinically significant corrected QT values using Fridericia's method (QTcF) will be summarized by treatment group. These presentations will include QTcF values > 450 to ≤ 480 , > 480 to ≤ 500 , and > 500 msec; or changes of > 30 to ≤ 60 or > 60 msec ([FDA, 2005](#)). For this categorization, the average of triplicate values will be utilized rather than the individual values comprising the triplicate measurement. An out-of-range categorical tabulation will also be presented for the subgroup of U.S subjects.

Additionally, a distribution plot of QTcF over time will be presented as an aid in identification of any possible time trend and outliers.

A substudy to evaluate the effect of tavapadon on the QT interval using C-QT modelling is also included in this trial. Matched triplicate ECGs and plasma tavapadon concentrations that are collected at preselected sites will be used to characterize the effects of tavapadon on the QT interval. The analysis plan is summarized separately.

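### SAP 4.2 lets an unscheduled repeat displace the scheduled post-baseline laboratory or ECG value in some by-visit summaries; scheduled records should come first

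*SAP*

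**What the plan says.** SAP 4.2 keeps scheduled laboratory data at their nominal visit but assigns early-termination and unscheduled visits to the Table 3 windows by study day. Other assessments are windowed by study day through Week 22. At Weeks 26 and 27 the nominal visit is used, except for early-termination and unscheduled records.

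For several records in one window, SAP 4.2 gives these rules in order:

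- Different dates: "the result closest to the analysis visit target day will be used for summary presentations".
- Equal distance: "If two measurements have the same distance to the target day, the later value will be used".
- Same date: an average record is used where one applies, and among several averages the one from scheduled measurements. Otherwise: "If no averages exist, the last record as determined by the time collected will be used".

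The protocol generates such records. Section 8.3.7 says that clinically significantly abnormal laboratory tests "should be repeated until the values return to normal, to baseline, or are no longer considered clinically significant". Section 8.3.6 says of ECGs: "The ECG will be repeated if any results are considered to be clinically significant". Neither gives a time for the repeat.

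SAP 5.14.5 and 5.14.7 summarise laboratory and ECG results by treatment group and visit. In the ECG paragraph of SAP 4.1.7, on baseline, the SAP takes the opposite line: "Scheduled records will be selected over unscheduled records if a tie breaker is needed".

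**The concern.** A repeat ordered because the scheduled result was abnormal enters the same window and competes with that result. It is always the later of the two, so the equal-distance rule and the same-date rule both favour it. Whether a value stays in the by-visit summary can therefore depend on what the value was, and the displacement tends toward normal. If one arm has more clinically significant abnormalities, it stands to lose more of them from its visit means and changes from baseline. The SAP already prefers the scheduled record for an ECG baseline tie and among same-date averages. The post-baseline single value is the gap.

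**Working it through.** The plan states no figure on this point, so the check is an enumeration of the rule.

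**Inputs.** Scheduled treatment visits may fall within 3 days either side of target (protocol Table 2), which gives seven allowed offsets, s = −3 to +3. Safety laboratory samples are scheduled after baseline at Weeks 11, 22 and 27, and ECGs at Weeks 5, 11, 14, 22 and 27. Windows come from SAP Table 3. The lag r in days from scheduled test to repeat is not in the documents, so each value is shown.

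**Same date (r = 0).** With no average record the last reading is used, so a repeated single value replaces the scheduled one on all 7 of 7 visit days. Post-baseline ECGs are single at non-US sites and triplicate at US sites (protocol 8.3.6). A same-date repeat therefore replaces the scheduled ECG at a non-US site, while at a US site the scheduled triplicate average is kept.

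**Later date (r ≥ 1).** The repeat lies at offset s + r and is chosen when |s + r| ≤ |s|.

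- If s ≥ 0, then s + r > s, so the repeat never wins.
- If s < 0, the condition becomes r ≤ 2|s|: up to 2 days for s = −1, 4 days for s = −2 and 6 days for s = −3.

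A winning repeat lies within 3 days of target, so it is inside the window at every visit listed.

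| Lag r (days) | Offsets at which the repeat wins | Share of allowed days |
|---|---|---|
| 1–2 | −1, −2, −3 | 3/7 (43%) |
| 3–4 | −2, −3 | 2/7 (29%) |
| 5–6 | −3 | 1/7 (14%) |
| 7 or more | none | 0 |

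The equal-distance rule decides only the mirror cases: s = −1 with r = 2, s = −2 with r = 4, and s = −3 with r = 6. A visit earlier than the protocol allows can be displaced at longer lags; at s = −7, up to 14 days if both records share a window.

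**Averaged over assumed lags**, with visit days uniform over the seven offsets and lags uniform over the range (both assumptions):

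- lags 1–3: (3+3+2)/21 = 8/21 (38%)
- lags 1–7: (3+3+2+2+1+1+0)/49 = 12/49 (24%)
- lags 1–14: 12/98 (12%)

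**Illustrative size for QTcF (all inputs assumed).** Suppose 2% to 6% of non-US subjects in an arm have a +40 ms change that reads +10 ms on a same-date single repeat. The non-US visit mean is then understated by 0.02 × 30 = 0.6 ms to 0.06 × 30 = 1.8 ms. Taking the roughly 240 subjects expected in the US substudy out of 522 (protocol 10.7.8 and 9.2), the non-US share is 282/522 = 0.54. The whole-arm understatement is about 0.3 to 1.0 ms. This is an upper-end case, because it assumes every such change is judged clinically significant and repeated the same day.

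**Efficacy.** Take Visit 10 on Day 179 and an early-termination assessment on Day 182. Both fall in the Week 26 window (169–185), at distances 3 and 0, so the early-termination record is selected. SAP 5.9.1 censors data after treatment discontinuation but does not say whether that comes before window selection. If windowing comes first and the selected record is then censored, the Day 179 score is lost.

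**The case against.** The strongest answer is that the rule turns on distance from target, not on recency. On 4 of the 7 allowed visit days no later-day repeat can win, and within the protocol tolerance none wins from a 7-day lag on. Laboratory values are read against a central laboratory's ranges (SAP 5.14.5), so a repeat prompted by a central result must wait for it; the short lags with the largest shares are not documented. Additional ECGs and tests are also allowed at the investigator's discretion (protocol 8.3.6 and Appendix 2), so not every unscheduled record is a retest of an abnormal value. A repeat may also correct an artefact. All of this stands, and it limits how often displacement occurs.

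The abnormal values are also kept elsewhere. The laboratory shift tables use the worst grade, or the maximum and minimum with unscheduled results included. The hepatic and QTcF category tables count any post-baseline occurrence, and the listings show individual results (SAP 5.14.5, 5.14.7). That stands too, and it confines the point to by-visit descriptive summaries.

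A reader might infer that abnormal outliers vanish from the liver distribution plots and from the QTcF plot, of which the SAP says that "a distribution plot of QTcF over time will be presented as an aid in identification of any possible time trend and outliers". The documents do not support that: neither section says the plots use one selected record per window.

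None of this answers the same-date case, where replacement of a single value with no average record is certain under the rule as written.

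**Conclusion.** The point holds in a limited form. An unscheduled repeat can displace the scheduled post-baseline value in the by-visit laboratory and ECG summaries: always for a same-date single value with no average record, and for a later-day repeat only under the timing condition shown above. The tendency toward normal values follows from the protocol's reasons for repeating. The per-lag shares follow from the SAP rule and the ±3-day tolerance, counting the seven visit days equally. The averaged shares and the QTcF figures rest on assumed timing and rates, and the actual frequency is unknown.

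Two stronger readings should be resisted. One is that a drug effect on safety is hidden: the documents show only that by-visit means could be shifted, and the outputs built to detect abnormal values are unaffected. The other is that the primary endpoint is compromised: the efficacy example needs an unusual sequence of dates and an assumed order of windowing and censoring. It is a reason to state the order, not evidence of bias. The change is worth making because it is cheap and agrees with what the SAP does elsewhere.

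**What to change.** Keep the present rules in SAP 4.2, including the average-record rules that duplicate vital signs and triplicate ECGs rely on, and add ahead of them:

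> If a window contains a non-missing scheduled record (or the average of scheduled replicates), it is used in preference to unscheduled, repeat or early-termination records, including on the same date. The closest-to-target and later-value rules then apply only among scheduled records, or among unscheduled/early-termination records when no scheduled record exists. For efficacy data, censoring under 5.9.1 is applied before window selection. All records continue to count in worst-value, any-occurrence and shift tables.

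Adding to the rules, not replacing them, also leaves a way to choose when two scheduled visits share a window. For example, a Week 11 ECG on Day 87 would fall in the Week 14 window (87–111).

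The cost is one paragraph of SAP text and a change to the record-selection code, with no new data. The small downside is that a scheduled reading that was a technical artefact stays in the by-visit summary unless it is invalidated at source.
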